8. TREATMENT OF PARTICIPANTS

8.1. Interventions

8.1.1. Interventions

This domain has two interventions:

- Commencement of prophylactic antibiotics (Arm A)
- Commencement of immunoglobulin replacement (Arm B)

8.1.2. Commencement of prophylactic antibiotics (Arm A)

Participants will be treated with once daily trimethoprim-sulfamethoxazole (co-trimoxazole) 160mg/800mg, with dose adjustments as listed below, from study day 1. For patients with hypersensitivity to co-trimoxazole, or who are taking a medication with potential for a significant interaction with co-trimoxazole as outlined below, 100mg doxycycline daily will be permitted as an alternative prophylactic antibiotic. If participants encounter cytopenias which are exacerbated by the study antibiotics, participants can be switched to the other antibiotic. Participants must be able to tolerate at least one of the study antibiotics to be eligible for entry into the study.

Medications which cannot be administered with co-trimoxazole include (but are not limited to): antiarrhythmics (dofetilide, amiodarone), antivirals (amantadine/memantine, lamivudine), antineoplastics (paclitaxel), antibiotics (dapsone). Co-trimoxazole may increase the effect of the following agents, and increased monitoring of their drug levels and/or effect is required if co-administered with co-trimoxazole: digoxin, phenytoin, warfarin, oral hypoglycaemics (repaglinide, rosiglitazone, pioglitazone, glipizide), methotrexate, drugs that cause potassium retention (such as ACE inhibitors) and cyclosporin (increased monitoring of renal function).

Medications which cannot be administered with doxycycline include (but are not limited to): isotretinoin, etretinate and methoxyflurane. Doxycycline may increase the effect of the following agents, and increased monitoring of drug levels and/or effect is required if co-administered with doxycycline: warfarin, cyclosporin, phenytoin.

8.1.2.1. *Co-trimoxazole dose adjustments for cytopenias and renal impairment*

For participants with grade 2 or greater anaemia, neutropenia or thrombocytopenia, whether attributed to concomitant medications, underlying haematologic disorder or co-trimoxazole itself,

the dose of co-trimoxazole may be reduced by 50% (to 80/400mg daily) at the discretion of the investigator.

Co-trimoxazole dose will be adjusted for participants with renal impairment, defined by eGFR (or, if available, measured creatinine clearance)

eGFR or creatinine clearance	Dose
> 50 mL/Min	Full dose (160/800mg)
30 to 50 mL/Min	50% dose reduction (to 80/400mg)
< 30 mL/Min	Consider switching to doxycycline, or discontinue study treatment

8.1.3. Commencement of immunoglobulin replacement (Arm B)

8.1.3.1. *Intravenous immunoglobulin (IVIg)*

Participants will receive monthly (every 4 weeks \pm 1 week) intravenous immunoglobulin at a dose of 0.4g/kg, modified to achieve an IgG trough level of at least lower limit of age-specific serum IgG reference range. In the first month of therapy, if IgG <4g/L then an additional (loading) dose of 0.4g/kg may be given at the clinician's discretion.

8.1.3.2. *Subcutaneous immunoglobulin (SCIg)*

Subcutaneous immunoglobulin weekly may be used in patients who meet local criteria for home-based self-administration in centres with established SCIg programs. Dosing is usually given at 100mg/kg/week, modified to achieve an IgG steady state level of at least the lower limit of the serum reference range. A loading IVIg dose may be given in the first month if required.

Study participants may transition from IVIg to SCIg, or vice versa, using a conversion factor of 1:1 for total monthly IV to SC dosing. Where IVIg is used in this protocol, unless explicitly stated, it shall be taken to include SCIg.

8.1.4. Cross-over

If a participant on the prophylactic antibiotic intervention arm (Arm A) experiences a Grade 3 or higher infectious complication, they may commence IgRT, as directed by their treating clinician.

In the absence of a Grade 3 or higher infectious complication, patients will stay on their assigned treatment. However, the treating clinician may start IgRT if this is deemed in the participant's best interest. This will not be regarded as an event for EFS in the primary analysis, however it will be recorded on the relevant eCRF for the purposes of supplementary analyses.

For participants on the immunoglobulin replacement (Arm B) who develop a grade 3 or higher infection, their subsequent treatment will be according to standard care as directed by their treating clinician.

In these situations, trial participation will not end and the participant will continue to follow the schedule of assessments until M12, except in the case of patients who also choose to withdraw from the study.

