1. DOMAIN SUMMARY

1.1. Domain Summary

Strata	Myeloma, Non-Hodgkin Lymphoma and Chronic Lymphocytic Leukaemia
Domain-specific inclusion criteria	None.
Domain-specific exclusion criteria	
Exclusion Criteria
 
Patients will not be eligible for this domain if they fulfil any of the following criteria:
 
 1. Prior or planned allogeneic haematopoietic stem cell transplantation. 2. Already receiving systemic antibiotic prophylaxis for the purpose of preventing bacterial infection (NB: patients may receive antiviral, antifungal and PJP prophylaxis). 3. Received immunoglobulin replacement in the preceding three months. 4. Objection to receiving immunoglobulin products. 5. Known history of IgA deficiency with anti-IgA. 6. History of severe allergy to immunoglobulin products. 7. Current active infection requiring systemic antibiotics. 8. Allergy or intolerance of all domain antibiotic options. 9. Pregnant or breastfeeding. 10. Severe renal impairment (estimated or measured creatinine clearance of < 30 mL/min). 11. Previous splenectomy. 12. Previous participation in this domain. 13. Treating team deems enrolment in the domain is not in the best interest of the patient.
Interventions to be compared	
Arm A: Start prophylactic oral antibiotics: Once daily trimethoprim-sulfamethoxazole (co-trimoxazole) 160mg/800mg.
 
NB: Doxycycline 100mg daily as an alternative for patients with hypersensitivity to co-trimoxazole.
 
Arm B: Start immunoglobulin replacement IVIg every 4 weeks \pm 1 week at a dose of 0.4g/kg, modified to achieve an IgG trough level of at least lower limit of age-specific serum IgG reference range; or SC Ig, weekly, may be used in patients who meet local criteria for home-based self-administration in centres with established SC Ig programs. Dosing is usually given at 100mg/kg/week, modified to achieve an IgG steady state level of at least the lower limit of the serum reference range. A loading IVIg dose may be given in the first month if required.
 
Planned treatment duration for all arms (A and B) is 12 months.

Trial hypotheses	1. Prophylactic oral antibiotics are non-inferior to Ig replacement for the prevention of severe, and/or recurrent infection in patients with secondary hypogammaglobulinaemia due to B-cell malignancies.
Primary outcome measure	Primary RATIONAL-PT Endpoint: refer to RATIONAL-PT Core Protocol

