4.3. The need for a trial comparing IgRT with prophylactic antibiotics

Our current treatment decisions on whether to use IgRT or prophylactic antibiotics in patients with acquired hypogammaglobulinaemia secondary to haematological malignancies are not evidence-based because there is limited data on efficacy of IgRT or prophylactic antibiotics, and the available trial evidence is limited by small patient numbers, risk of bias and lack of contemporaneous and comparative data. These have been identified as priority evidence gaps in the recent Australian Medical Services Advisory Committee review of the cost-effectiveness of IgRT, specifically:

- Consideration for eligibility criteria used in Europe (trial of antibiotics before starting Ig therapy)
- Cost effectiveness of Ig in NHL (the largest patient group), as there are no Ig studies in these patients.

Therefore, a clinical trial is required to evaluate the comparative efficacy, safety and cost-effectiveness of prophylactic antibiotics compared with IgRT.

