4.3.1. Domain hypothesis

Prophylactic oral antibiotics are non-inferior to IgRT replacement for the prevention of severe, and/or recurrent infection in patients with secondary hypogammaglobulinaemia due to B-cell malignancies.

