5. DOMAIN OBJECTIVES

5.1. Aims

The aim of this domain is to determine the effectiveness of prophylactic antibiotics compared to IgRT in patients with haematological malignancies and acquired hypogammaglobulinaemia on event-free survival (as defined in the core protocol).

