6. DOMAIN DESIGN

This RATIONAL Platform Trial is an investigator-initiated open-label, randomised controlled adaptive platform trial open in multiple sites. The platform design allows many treatment approaches to be tested simultaneously on different patient subpopulations, within the same framework, and for pre-specified interim analyses that can be used to stop recruitment early to arms showing insufficient evidence of efficacy or overwhelming evidence of efficacy. The platform allows the addition of new domains via protocol amendments and DSAs to answer new questions of interest, including different treatments or patient groups. Details of the overall platform trial design are included in the Core Protocol.

The Start Ig DSA is one of multiple domains in the RATIONAL Platform trial. This domain is testing whether commencing prophylactic antibiotics is non-inferior to the standard dose of IgRT in patients with secondary hypogammaglobulinemia due to haematological malignancies.

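### Does IgRT given at clinician discretion in the antibiotic arm leave the non-inferiority hypothesis and the primary analysis asking different questions?

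*Protocol*

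**What the plan says.** The formal hypothesis in 4.3.1 reads "Prophylactic oral antibiotics are non-inferior to IgRT replacement for the prevention of severe, and/or recurrent infection in patients", and the summary table in 1.1 has nearly the same sentence. The aim in 5.1 begins "The aim of this domain is to determine the effectiveness of prophylactic antibiotics compared to IgRT in patients with haematological malignancies" and names event-free survival (EFS) as the outcome.

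Section 6 words the question differently: "This domain is testing whether commencing prophylactic antibiotics is non-inferior to the standard dose of IgRT". Section 8.1.1 names both interventions as the commencement of a treatment. In 1.1 the arm descriptions under the interventions to be compared both begin with the word Start.

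Section 8.1.4 deals with IgRT in Arm A. After a Grade 3 or higher infection, IgRT may be started. Without one, participants stay on their assigned treatment, with an exception: "However, the treating clinician may start IgRT if this is deemed in the" participant's best interest. Of that discretionary use it says "This will not be regarded as an event for EFS in the primary analysis, however it will be recorded on the relevant eCRF", for use in supplementary analyses. Follow-up continues to month 12 in either case, unless the participant withdraws from the study.

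The endpoint definition is left to the Core Protocol (9.1), and the statistical methods to the Master Statistical Analysis Appendix and the domain-specific SAP (section 12).

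**The concern.** Read alone, the sentences in 1.1, 4.3.1 and 5.1 seem to be about antibiotics as a treatment. The rule in 8.1.4 seems to produce a comparison of two policies: start antibiotics and add IgRT if the clinician wishes, against start IgRT. On that reading the document states one question and analyses another.

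This would matter more here than in most trials. The rescue treatment is the comparator itself and the claim is non-inferiority. If antibiotics alone were worse, IgRT given in Arm A before any event would shrink the observed difference and make non-inferiority easier to declare. A positive result would then support the starting policy, but not a statement that antibiotics by themselves are as good as IgRT.

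**Working it through.** **No figure to reproduce.** The protocol gives no margin, error rate, sample size, event count or expected cross-over rate. The check is a comparison of texts, followed by an illustration on assumed inputs.

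**Step 1: the texts side by side.**

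| Place | What is compared | Excludes later IgRT? |
|---|---|---|
| 1.1 and 4.3.1, hypothesis | antibiotics against Ig replacement | no |
| 5.1, aim | effectiveness of antibiotics against IgRT | no |
| 1.1, arm descriptions | starting antibiotics; starting Ig | no |
| 6, design | commencing antibiotics against standard-dose IgRT | no |
| 8.1.1, arms | commencement of each treatment | no |
| 8.1.4, cross-over | later IgRT allowed in Arm A | expressly allows it |

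No sentence describes antibiotics without later IgRT. The hypothesis in 1.1 stands in the same table as the two Start labels. Naming the randomised treatment in a hypothesis is ordinary shorthand for the arm. The evidence gap cited in 4.3, a trial of antibiotics before Ig therapy, is also a question about strategy.

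**Step 2: what 8.1.4 settles.** It settles that discretionary IgRT is not an EFS event. It does not say whether time after the switch is counted or censored. Follow-up to month 12, with the switch reserved for supplementary analyses, makes counting the likely reading, but that is an inference. Only IgRT before a first event matters here. If a Grade 3 infection is itself an EFS event (the definition is not shown), IgRT given after it cannot affect a time-to-first-event analysis.

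**Step 3: size, on assumptions.** Assumed: 12-month risk 25% on IgRT (the approximate pilot share with a Grade 3 or higher infection, section 4.2.7, used as a stand-in for EFS); 35% on antibiotics alone, so worse by exactly an assumed 10-point margin; one-sided 2.5%; 80% power under equality; constant hazards; the IgRT hazard after a switch; all follow-up counted.

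- Sample size per arm: (1.960 + 0.842)² × 2 × 0.25 × 0.75 / 0.10² = 294.3, rounded up to 295.
- Hazards per 12 months: λB = −ln 0.75 = 0.2877; λA = −ln 0.65 = 0.4308; switching μ = −ln(1 − c), where c is the proportion that would switch by 12 months if no events occurred.
- Event-free in Arm A at 12 months: exp(−(λA+μ)) + [μ/(λA+μ−λB)] × [exp(−λB) − exp(−(λA+μ))].
- Probability of declaring non-inferiority: Φ((0.10 − d)/SE − 1.96), with d the risk difference and SE unpooled.

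| c | Event-free, not switched | Event-free, switched | Arm A risk | d | P(declare NI) |
|---|---|---|---|---|---|
| 0 | 0.650 | 0 | 0.350 | 0.100 | 2.5% |
| 10% | 0.585 | 0.070 | 0.345 | 0.095 | 3.4% |
| 20% | 0.520 | 0.140 | 0.340 | 0.090 | 4.6% |
| 30% | 0.455 | 0.211 | 0.334 | 0.084 | 6.1% |

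At 30% switching, margins of 7.5 points (524 per arm) and 12.5 points (189 per arm) give 6.2% and 6.1%.

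On a hazard-ratio scale with an assumed margin of 1.5, a no-rescue hazard ratio of 1.5 is estimated as 1.469 when 10% of Arm A switch before an event, and as 1.437 when 20% do. With D events, P = Φ(ln(1.5/HR) × √(D/4) − 1.96):

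- D = 200: 3.5% and 4.9%. Power under equality is Φ(0.4055 × 7.071 − 1.96) = 81.8%.
- D = 100: 3.2% and 4.0%. Power is only Φ(0.4055 × 5 − 1.96) = 53%, so 200 events is the more coherent setting for this margin.

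If the arms are truly equal (λA = λB), the event-free formula gives exp(−λB) whatever μ is, so nothing moves. This needs the hazard after a switch to equal that of IgRT alone. Section 8.1.4 speaks of starting IgRT and does not say that antibiotics stop.

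**Step 4: what rewording would change.** The event definition, follow-up, primary analysis and non-inferiority decision would all stay the same. So would every row of the table above.

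**The case for a change.** The strongest case for a change is that the hypothesis sentence is the one a final report will echo, and it names antibiotics, not a policy of starting them. Dilution by the comparator favours the claim, the sentences involved all stand in this document, and a wording change costs no power.

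Part of this stands. The wording is uneven, 8.1.4 is silent on time after a switch, and the direction of the effect is right if antibiotics alone are worse.

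The rest does not carry. The claim that there are two questions depends on reading a no-rescue condition into sentences that contain none. Section 6 differs from 4.3.1 mainly by the word commencing and does not mention later IgRT either, so a hypothesis naming later IgRT would be new text, not the plan's own wording carried across. Such a rewrite would also be partial. Discontinuation with follow-up to month 12 (8.1.6) and low-dose co-trimoxazole continued for PJP prophylaxis (8.1.7) also separate the policy from the treatment, and nobody would list them all in a hypothesis. A supplementary analysis weighted for IgRT start and a table of cross-overs by arm are matters for the domain-specific SAP, which is not shown. Section 8.1.4 already provides for the data to be recorded and for supplementary analyses.

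**Conclusion.** No change to the plan follows. The document is most naturally read as comparing starting strategies, and a primary analysis that does not count discretionary IgRT as an event fits that reading. The uneven wording is editorial. The sponsor may carry starting or commencing into 1.1, 4.3.1 and 5.1 so that the conclusion is phrased in the same way, but nothing in the analysis depends on it.

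The excess chance of declaring non-inferiority against a no-rescue question is about 1 to 2 percentage points at 10–20% switching (3.4–4.6% against 2.5%). It rests on an assumed margin, sample size, error rate and switching rate, on a pilot infection share standing in for the EFS risk, and on counting time after the switch. None of these is given or confirmed in the document. Against the strategy question it is not an error at all.

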8.1.5. Duration of therapy

Participants will remain on assigned treatment for 12 months. Participants do not need to stop their trial-assigned treatment at 12 months, but all treatment decisions including for prevention of infection after completion of trial treatment (at 12 months from Day 1 of study) will be managed by the participant's treating clinician.

8.1.6. Discontinuation of study assigned treatment protocol

Site investigators/clinicians may discontinue a patient from their assigned trial treatment if this is no longer in the participant's best interest. Reasons for treatment discontinuation may include:

- Grade 3 or higher adverse event
- Grade 3 or higher infectious complication
- Unrelated medical illness or clinical condition representing potential risk, such as change to therapy for underlying malignancy
- Participant's request
- Poor compliance
- Participant is no longer deemed eligible to participate (e.g. if they develop a contraindication to treatment allocation)

If a participant is discontinued from the assigned treatment protocol for any reason, the end-of-treatment (EOT) visit assessments should be completed 4 weeks (+/- 7 days) after the final administration of the participant's assigned treatment. Trial participation will not end and the participant will continue to follow the schedule of assessments until M12.

8.1.7. Concomitant care

All other aspects of care, including other antimicrobial prophylaxis (including antivirals, antifungals) and vaccinations, will be according to usual care and local practice. For example, patients already taking low-dose (80mg/400mg) daily or intermittent (three times a week) co-trimoxazole for *Pneumocystis jirovecii* pneumonia (PJP) prophylaxis may continue, if necessary with a dose increase if allocated to Arm A. Higher doses of PJP prophylaxis are not permitted in the immunoglobulin treatment arm.

It is recommended that all participants receive routine vaccinations, including pneumococcal, influenza and COVID-19 vaccines, as part of their usual care, and have measurement of pre- and post-vaccination pneumococcal responses, where polysaccharide pneumococcal vaccine is due to be given on study.

Patients who are commenced on therapy to treat underlying malignancy may continue on the study. Patients may receive granulocyte colony stimulating factor (G-CSF) for prophylaxis or treatment of neutropenia according to local guidelines.

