7.2.2. Domain exclusion criteria

1. Prior or planned allogeneic haematopoietic stem cell transplantation.
2. Already receiving systemic antibiotic prophylaxis for the purpose of preventing bacterial infection (NB: patients may receive antiviral, antifungal and PJP prophylaxis).
3. Received immunoglobulin replacement in the preceding three months.
4. Objection to receiving immunoglobulin products.
5. Known history of IgA deficiency with anti-IgA.
6. History of severe allergy to immunoglobulin products.
7. Current active infection requiring systemic antibiotics.
8. Allergy or intolerance of all domain antibiotic options.
9. Pregnant or breastfeeding.
10. Severe renal impairment (estimated or measured creatinine clearance of < 30 mL/min).
11. Previous splenectomy.
12. Previous participation in this domain.
13. Treating team deems enrolment in the domain is not in the best interest of the patient.

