7.3. Randomisation

Randomisation will occur following confirmation of participant eligibility for the domain, between the baseline and Start Domain Day 1 visit. Randomisation will be conducted through a password-protected secure website using a central randomisation programme. Eligibility for randomisation will be assessed with reference to the Platform-level and Domain-level inclusion and exclusion criteria and there will be no exception to eligibility requirements at the time of randomisation.

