10. ASSESSMENTS AND FOLLOW-UP

10.1. Domain Schedule of Assessments

Please see Domain Schedule of Assessments over page. This is in addition to the Schedule of Assessments in the Core Protocol.

All participants enrolled in the platform and any one of the domains are to be followed according to the Schedule of Assessments in the core platform protocol. The following additional assessments are to be completed for all participants enrolled in this domain. All visits for the domain must align with the core protocol visits and visit windows, for example the Month 1 visit on the domain is the Month 1 visit on the platform schedule of assessments.

Period	Screening	Treatment Period													Follow-up
Procedure	Visit BL	Visit D1*	Visit M1	Visit M2	Visit M3	Visit M4	Visit M5	Visit M6	Visit M7	Visit M8	Visit M9	Visit M10	Visit M11	Visit M12/EOT	
Domain Informed Consent	X														
Treatment details [#]	X														
Domain eligibility assessment	X														

*D1 is Day 1 of trial treatment. BL and D1 assessment may occur on the same day. D1 must occur no more than 7 days after randomisation.

[#]Updated information on treatment for underlying malignancy if this has changed from platform enrolment

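### Exclusion 2 sets no dose limit on PJP prophylaxis, so a patient already taking the Arm A co-trimoxazole regimen can enter a domain that compares starting antibiotics with starting immunoglobulin

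*Protocol*

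**What the plan says.** Four parts of the Protocol bear on this.

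- **Eligibility.** Exclusion 2 in 7.2.2 bars a patient who is "Already receiving systemic antibiotic prophylaxis for the purpose of preventing bacterial infection (NB: patients may receive antiviral, antifungal and PJP prophylaxis"). Section 1.1 repeats it. Neither place gives a dose. Section 7.2.1 lists no domain inclusion criteria and 7.2.3 no intervention exclusions.
- **Arm A treatment.** Section 8.1.2: "Participants will be treated with once daily trimethoprim-sulfamethoxazole (co-trimoxazole) 160mg/800mg, with dose adjustments as listed below, from study day 1".
- **PJP prophylaxis on study.** Section 8.1.7 says that "patients already taking low-dose (80mg/400mg) daily or intermittent (three times a week) co-trimoxazole for" PJP "may continue, if necessary with a dose increase if allocated to Arm A". It then adds: "Higher doses of PJP prophylaxis are not permitted in the immunoglobulin treatment arm".
- **Sequence.** Section 7.3: "Randomisation will occur following confirmation of participant eligibility for the domain, between the baseline and Start Domain Day 1 visit", and "there will be no exception to eligibility requirements at the time of randomisation". Section 10.1 adds that "D1 must occur no more than 7 days after randomisation".

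**The concern.** Exclusion 2 sorts patients by why they take an antibiotic. Section 8.1.7 sorts them by how much they take, but only in Arm B and only after allocation. Co-trimoxazole 160/800 mg daily therefore excludes a patient if it was prescribed against bacteria and does not if it was prescribed against PJP, although it is the same drug at the same dose as Arm A.

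What is at stake is the question put to such a patient. Sections 6 and 8.1.1 describe the domain as a comparison of commencing antibiotics with commencing immunoglobulin. Someone who already takes the Arm A regimen has nothing to commence in Arm A, and in Arm B undergoes a dose cut as well as starting immunoglobulin. Section 9 describes patients who qualify for immunoglobulin through recurrent or severe infections or a low IgG. A patient whose infections occurred on 160/800 mg daily could thus be allocated to the same drug and dose as the trial intervention.

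**Working it through.** **Inputs**

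- Arm A full dose: 160/800 mg once daily (8.1.2).
- PJP regimens that may continue: 80/400 mg daily, or three times a week (8.1.7). The dose per intake of the three-times-weekly regimen is not stated, so both 160/800 mg and 80/400 mg are tried as assumptions.
- The plan's own figure: 8.1.2.1 calls 80/400 mg daily a 50% reduction of the full dose.

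**Weekly dose = dose per intake × intakes per week (trimethoprim/sulfamethoxazole)**

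- 160/800 mg daily: 160 × 7 / 800 × 7 = 1120/5600 mg
- 80/400 mg daily: 80 × 7 / 400 × 7 = 560/2800 mg
- 160/800 mg three times a week (assumed): 160 × 3 / 800 × 3 = 480/2400 mg
- 80/400 mg three times a week (assumed): 80 × 3 / 400 × 3 = 240/1200 mg

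Check against the plan: 1 − 560/1120 = 50.0%, as 8.1.2.1 states.

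**Change after allocation for a patient who enters on 160/800 mg daily for PJP**

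| Allocation | Weekly trimethoprim | Change |
|---|---|---|
| Arm A, full dose | 1120 → 1120 mg | 0% |
| Arm B, to 80/400 mg daily | 1120 → 560 mg | −560/1120 = −50.0% |
| Arm B, to 160/800 mg three times a week (assumed) | 1120 → 480 mg | −640/1120 = −57.1% |
| Arm B, to 80/400 mg three times a week (assumed) | 1120 → 240 mg | −880/1120 = −78.6% |

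The smallest cut that satisfies 8.1.7 is 50%, whichever tablet strength is meant.

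**Does this patient pass the domain criteria?** Exclusion 2 does not apply, because the purpose is PJP. No other listed exclusion refers to the dose of an existing prophylactic drug. Exclusion 13 lets the treating team decline enrolment but sets no dose. Under 7.3 eligibility is settled before allocation, and the cap in 8.1.7 is not one of the criteria.

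**After the fix.** If exclusion 2 carried the 8.1.7 limit, every patient on PJP co-trimoxazole would enter at or below a dose allowed in Arm B. The cut forced by allocation would be 0%, and a patient going to full-dose Arm A would step up from a lower dose.

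**The case against.** A reader might infer that exclusion 2 and 8.1.7 contradict each other. They do not: one says who may enter, the other what may be taken in Arm B, and a patient who steps down obeys both. Rules on concomitant drugs that depend on allocation are ordinary, and a cap in the immunoglobulin arm is sensible. Nor is the cap hidden. It can be read before consent, and a team that thinks the higher dose must continue can use exclusion 13. All of that stands. It still leaves a discretionary judgement doing the work of an eligibility rule.

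A reader might also infer that Arm B patients lose half their protection against PJP. The documents do not support that. The arithmetic concerns milligrams, and the regimens that 8.1.7 allows are ones it names as PJP prophylaxis.

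The zero change in Arm A holds at full dose only. Section 8.1.2.1 halves the dose at an eGFR of 30 to 50 mL/min and allows halving for grade 2 or greater cytopenias. Section 8.1.2 permits doxycycline where there is hypersensitivity or an interaction. That limit is accepted.

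Finally, no one is shown to take 160/800 mg daily for PJP; the regimens that 8.1.7 names as already in use are lower. Platform-level criteria, which 7.2 makes a precondition, might also remove these patients. Both points limit the weight and the confidence of the finding. Neither supplies the missing dose limit in this appendix, and 8.1.7 itself foresees higher PJP doses by forbidding them in Arm B.

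**Conclusion.** The point holds as a cheap improvement, with moderate confidence. As this appendix is written, a patient on the Arm A regimen for PJP is eligible, has no change at full Arm A dose, and must reduce co-trimoxazole by at least 50% in Arm B. For that patient the domain tests continuing against stepping down and adding immunoglobulin.

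It would be tempting to go on to say that the treatment comparison as a whole is distorted. The documents do not support that. The cap limits co-trimoxazole in Arm B for these patients exactly as for any other patient on PJP prophylaxis, so the dose difference between the arms on study is preserved. The number of patients is not given, no effect on the endpoint can be computed, and the trial-level effect is probably small.

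The conclusion assumes that the Core Protocol, which is not at hand, has no criterion that already excludes these patients, and that exclusion 13 is not applied to all of them.

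**What to change.** In exclusion 2, in both 7.2.2 and 1.1, add that patients who take or need co-trimoxazole PJP prophylaxis above the doses allowed in 8.1.7 are not eligible. This turns a rule that now takes effect after allocation, in one arm, into one that applies to everyone before randomisation.

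For that cross-reference to be usable, 8.1.7 should also state the tablet strength of the three-times-weekly regimen. This is a clarification only: 160/800 mg three times a week gives 480/560 = 85.7% of the weekly dose of the permitted 80/400 mg daily, so the weekly maximum is the same on either reading.

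The cost is one line in two places and a few words in 8.1.7. The downside is that a few patients become ineligible or must change dose before entry.
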